- 5559 patients in Novartis-sponsored clinical trials
- 712 patients in the single patients use IND program for renal cell cancer
- 5474 in investigator-sponsored studies.
- In addition, healthy volunteer subjects have participated in the clinical pharmacology studies as described in [Section 5.2](#).

As of 30 SEP 2010, there are a total of 11 Phase III trials ongoing in the indications mRCC (1), advanced NET (2), breast cancer (3), TSC (2), DLBCL (1), gastric cancer (1) and hepatocellular carcinoma (1). One additional Phase III trial in the TCS will be starting later in Protocol: RAD001

2011. In addition, the Phase II SEGA in Tuberous Sclerosis study remains ongoing for follow-up.

Recent approvals of everolimus (Afinitor®) were based upon a Phase III, international, multicenter randomized, double-blind, placebo-controlled study [C2240] in patients with metastatic renal cell carcinoma (mRCC) whose disease had progressed despite prior treatment with VEGFR-TKI (vascular endothelial growth factor receptor tyrosine kinase inhibitor) therapy. Progression-free survival (PFS) assessed *via* a blinded, independent central review, was the primary endpoint. Secondary endpoints included safety, objective tumor response

In the pivotal, Phase III study [C2240], which included patients with advanced renal cell carcinoma, the most common adverse reactions (incidence $\geq 10\%$) were stomatitis, rash, fatigue, asthenia, diarrhea, anorexia, nausea, mucosal inflammation, vomiting, pneumonitis, cough, peripheral edema, infections, dry skin, epistaxis, pruritus, and dyspnea. The most common grade 3-4 adverse reactions (incidence $\geq 2\%$) were infections, stomatitis, fatigue, and pneumonitis. Non-infectious pneumonitis is a class effect of rapamycin derivatives, including Everolimus and some of these cases have been severe and on rare occasions, fatal outcomes have been observed. Everolimus has immunosuppressive properties and may predispose patients to bacterial, fungal, viral or protozoan infections, including infections with opportunistic pathogens. Localized and systemic infections, including pneumonia, other bacterial infections, invasive fungal infections, such as aspergillosis or candidiasis and viral infections including reactivation of hepatitis B virus, have been described in patients taking everolimus. Some of these infections have been severe (e.g. leading to respiratory or hepatic failure) and occasionally have had a fatal outcome

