The most common laboratory abnormalities (incidence $\geq 50\%$) were anemia, hypercholesterolemia, hypertriglyceridemia, hyperglycemia, lymphopenia, and increased creatinine. The most common grade 3/4 laboratory abnormalities (incidence $\geq 3\%$) were lymphopenia, hyperglycemia, anemia, hypophosphatemia, and hypercholesterolemia. Deaths due to acute respiratory failure (0.7%), infection (0.7%), and acute renal failure (0.4%) were

observed on the everolimus arm. The rates of treatment-emergent adverse reactions resulting in permanent discontinuation were 7% and 0% for the everolimus and placebo treatment groups, respectively. Safety data from study [C2240] are described in detail in [Section 6.5](#).

Overall, safety data available from completed, controlled and uncontrolled studies are consistent with the aforementioned findings of the Phase III trial. Everolimus is generally well tolerated at weekly and daily dose schedules. The safety profile is characterized by manageable adverse events (AEs). These AEs are generally reversible and non-cumulative.

Further detailed information regarding RAD001 clinical development, safety and efficacy is provided in the [Investigator's Brochure].

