3.2.3 Interruption or discontinuation of treatment

For patients who are unable to tolerate the protocol-specified dosing schedule, dose adjustments are permitted in order to keep the patient on study drug. If administration of RAD001 must be interrupted because of unacceptable toxicity, drug dosing will be interrupted or modified according to rules described in Table 3-1. Toxicity will be assessed using the NIH-NCI Common Terminology Criteria for Adverse Events, version 3.0 (CTCAEv3.0, (<http://ctep.cancer.gov/forms/CTCAEv3.pdf>)).

Table 3.0 RAD001 dose level modification guidelines

Dose level	Dose and schedule
0 (starting dose)	10 mg daily
-1	5 mg daily
-2	5 mg every other day

Table 3-1 Criteria for dose-modification in case of suspected RAD001 toxicity and re-initiation of RAD001 treatment

Toxicity	Actions
Non-hematological toxicity	
Grade 2 (except pneumonitis – refer to Table 3-2)	If the toxicity is tolerable to the patient, maintain the same dose. If the toxicity is intolerable to patient, interrupt RAD001 until recovery to grade ≤ 1 . Then reintroduce RAD001 at same dose. If event returns to grade 2, then interrupt RAD001 until recovery to grade ≤ 1 . Then reintroduce RAD001 at the lower dose level.
Grade 3 (except hyperlipidemia*) (except pneumonitis – refer to Table 3-2)	Interrupt RAD001 until recovery to grade ≤ 1 . Then reintroduce RAD001 at the lower dose level. For pneumonitis consider the use of a short course of corticosteroids.
Grade 4	Discontinue RAD001.
Hematological toxicity	
Grade 2 Thrombocytopenia (platelets $<75, \geq 50 \times 10^9/L$)	Interrupt RAD001 until recovery to grade ≤ 1 ($>75 \times 10^9/L$). Then reintroduce RAD001 at initial dose. If thrombocytopenia again returns to grade 2, interrupt RAD001 until recovery to grade ≤ 1 . Then reintroduce RAD001 at the lower dose level.
Grade 3 Thrombocytopenia (platelets $<50, \geq 25 \times 10^9/L$)	Interrupt RAD001 until recovery to grade ≤ 1 (platelets $\geq 75 \times 10^9/L$). Then resume RAD001 at one dose level lower. If grade 3 thrombocytopenia recurs, discontinue RAD001.
Grade 4 Thrombocytopenia (platelets $< 25 \times 10^9/L$)	Discontinue RAD001.

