3.2.5 Known Undesirable Side Effects of RAD001

The data described below reflect exposure to everolimus (n=274) and placebo (n=137) in a randomized phase III study for the treatment of metastatic renal cell carcinoma. In total, 165 patients were exposed to everolimus 10 mg/day for \geq 4 months. The median age of patients was 61 years (range 27 to 85). The most common adverse reactions (incidence \geq 10%) were stomatitis, rash, fatigue, asthenia, diarrhea, anorexia, nausea, mucosal inflammation, vomiting, cough, peripheral edema, infections, dry skin, epistaxis, pruritus, and dyspnoea. The most common grade 3-4 adverse reactions (incidence \geq 2%) were infections, stomatitis, fatigue, and pneumonitis.

The median duration of blinded study treatment was 141 days (range 19 to 451) for patients receiving everolimus and 60 days (range 21 to 295) for those receiving placebo. The rates of treatment-emergent adverse reactions resulting in permanent discontinuation were 7% and 0% for the everolimus and placebo treatment groups, respectively. Most treatment-emergent adverse reactions were grade 1 or 2 in severity. Grade 3 or 4 treatment-emergent adverse reactions were reported in 39% versus 7% of patients receiving everolimus and placebo, respectively. Deaths due to acute respiratory failure (0.7%), infection (0.7%), and acute renal failure (0.4%) were observed on the everolimus arm.

Everolimus has immunosuppressive properties and may predispose patients to bacterial, fungal, viral or protozoan infections, including infections with opportunistic pathogens. Localized and systemic infections, including pneumonia, other bacterial infections, invasive fungal infections, such as aspergillosis or candidiasis and viral infections including reactivation of hepatitis B virus, have been described in patients taking everolimus. Some of these infections have been severe (e.g. leading to respiratory or hepatic failure) and occasionally have had a fatal outcome.

Physicians and patients should be aware of the increased risk of infection with everolimus. Treat pre-existing infections prior to starting treatment with everolimus. While taking everolimus, be vigilant for symptoms and signs of infection; if a diagnosis of infection is made, institute appropriate treatment promptly and consider interruption or discontinuation of everolimus. If a diagnosis of invasive systemic fungal infection is made, discontinue everolimus and treat with appropriate antifungal therapy.

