3.4.3.1 Adverse events

Information about all adverse events, whether volunteered by the subject, discovered by investigator questioning, or detected through physical examination, laboratory test or other means, will be collected and recorded and followed as appropriate.

An adverse event is the appearance or worsening of any undesirable sign, symptom, or medical condition occurring after starting the study drug even if the event is not considered to be related to study drug. Medical conditions/diseases present before starting study drug are only considered adverse events if they worsen after starting study drug. Abnormal laboratory values or test results constitute adverse events only if they induce clinical signs or symptoms, are considered clinically significant, or require therapy.

The occurrence of adverse events should be sought by non-directive questioning of the patient at each visit during the study. Adverse events also may be detected when they are volunteered by the patient during or between visits or through physical examination, laboratory test, or other assessments. As far as possible, each adverse event should be evaluated to determine:

1. the severity grade (mild, moderate, severe) or (grade 1-4)
2. its relationship to the study drug(s) (suspected/not suspected)
3. its duration (start and end dates or if continuing at final exam)
4. action taken (no action taken; study drug dosage adjusted/temporarily interrupted; study drug permanently discontinued due to this adverse event; concomitant medication taken; non-drug therapy given; hospitalization/prolonged hospitalization)
5. whether it constitutes a serious adverse event (SAE)

All adverse events should be treated appropriately. Such treatment may include changes in study drug treatment including possible interruption or discontinuation, starting or stopping concomitant treatments, changes in the frequency or nature of assessments, hospitalization, or any other medically required intervention. Once an adverse event is detected, it should be followed until its resolution, and assessment should be made at each visit (or more frequently, if necessary) of any changes in severity, the suspected relationship to the study drug, the interventions required to treat it, and the outcome.

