3.4.6 Review of Adverse Event Rates

If the study has an increase of unexpected or expected Adverse Events grade 3 or 4 above the rate reported in the Investigational Brochure or package insert, the increase rate of AEs will be reported to the DSMC at the time of Identification. The Chair and PI will discuss the finding and proceed with a written course of action. Each quarterly report will indicate if the AE incidence is within the scope of the investigational brochure or package insert. If at any time the Investigator stops enrollment or stops the study due to safety issues the DSMC Chair and Administrator must be notified within 24 business hours via e-mail. The DSMC must receive a formal letter within 10 business days and the CHR must be notified.

If any of the above action occurs in multiple-institutional clinical trial coordinated by the UCSF-CCC, the Study Coordinator will insure that all participating sites are notified.

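### The adverse event rate review can miss an excess of grade 3–4 lymphopenia or anemia, because laboratory values that are asymptomatic, untreated and not judged significant are not counted

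*Combined protocol and SAP*

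**What the plan says.** Section 3.4.3.1 sets the counting rule for laboratory results: "Abnormal laboratory values or test results constitute adverse events only if they induce clinical signs or symptoms, are considered clinically significant, or require therapy". It has no grade threshold, and clinical significance is not defined.

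Sections 3.4.5.2 and 3.4.5.4 send grade 3–5 adverse events to the safety database. Under Section 3.4.6, the monitoring committee is told of an "increase of unexpected or expected Adverse Events grade 3 or 4 above the rate reported in the Investigational Brochure or package insert". The same section adds: "Each quarterly report will indicate if the AE incidence is within the scope of the investigational brochure or package insert". Neither sentence mentions graded laboratory values.

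The brochure itself is not among the documents. The protocol's summary of the phase III renal-cell study (Section 1.1.3.3) gives two lists. The most common grade 3–4 adverse reactions, at 2% or more, "were infections, stomatitis, fatigue, and pneumonitis". The grade 3/4 laboratory abnormalities, at 3% or more, form a separate list: they "were lymphopenia, hyperglycemia, anemia, hypophosphatemia, and hypercholesterolemia".

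Section 3.2.3 grades toxicity for dosing by CTCAE version 3.0. The hematological rows of Table 3-1 cover thrombocytopenia, neutropenia and febrile neutropenia. Lymphopenia and anemia have no row of their own.

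**The concern.** A rate comparison means something only if both sides count the same thing. Here the trial's count of laboratory toxicity passes through symptoms, treatment or investigator judgement. The reference, as the protocol summarises it, includes a list of laboratory abnormalities by grade. Section 3.4.6 does not say which list is the comparator.

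The exposure is greatest where a grade 3–4 value leads to no action written in the plan. Lymphopenia is named first among the reference study's grade 3/4 laboratory abnormalities, and Section 3.2.5 warns of infection through immunosuppression. Yet an asymptomatic, untreated grade 3 lymphocyte count that the investigator does not judge significant is not an adverse event, so it enters neither the rate review nor the grade 3–5 database entries. No later analysis fills the gap: safety is the first secondary objective in Section 2, but Section 6.1.4 plans no safety or laboratory summary.

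**Working it through.** **Step 1. Follow a grade 3–4 laboratory value through the plan.**

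- *Hyperglycemia, hypophosphatemia.* Table 3-1 interrupts drug for grade 3 non-hematological toxicity. Such a value would ordinarily be judged significant or be treated, so it would normally count.
- *Hypercholesterolemia.* The footnote to Table 3-1 refers grade 3 hyperlipidemia to medical therapy, so it would count.
- *Lymphopenia.* No row of its own and no listed action. It counts only if symptomatic, treated or judged significant.
- *Anemia.* No row of its own. The exposure is smaller on the judgement, not given in the documents, that severe anemia more often causes symptoms or is treated.

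So for three of the five listed abnormalities the filter probably removes little. Lymphopenia and, less so, anemia remain.

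**Step 2. The comparator determines the direction.**

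- Set against graded laboratory-abnormality rates, a filtered trial count is too low and an excess can be hidden.
- Set against an adverse-reaction list without laboratory terms, laboratory adverse events have no reference rate. They add to the trial's total and can suggest a false excess.
- Set against the overall figure in Section 3.2.5 ("Grade 3 or 4 treatment-emergent adverse reactions were reported in 39% versus 7% of patients receiving everolimus and placebo, respectively"), the direction is unknown, because the text does not say whether laboratory terms are included.

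**Step 3. Illustrate the size for the first case.** The plan gives no figure to reproduce. Only n = 60 (Section 6.1.3) and the 3% listing threshold (Section 1.1.3.3) come from the documents. The rest is assumed: a graded reference rate b, a true trial rate of 2b, a share f passing the filter, and a flag when the observed rate exceeds b. Section 3.4.6 states no margin or test.

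The expected counted rate is 2b × f. It equals b at f = 0.5, so on average a doubling disappears once half or fewer are counted. The chance of a flag is P(X > 60b), with X binomial(60, 2bf):

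| b | Flag when | f = 1 | f = 0.5 | f = 1/3 |
|---|---|---|---|---|
| 3% | X ≥ 2 | 0.88 | 0.54 | 0.34 |
| 5% | X ≥ 4 | 0.86 | 0.35 | 0.14 |
| 10% | X ≥ 7 | 0.97 | 0.39 | 0.10 |

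For b = 10%, the counted rates are 0.20, 0.10 and 0.067. The f = 0.5 column is also the false-flag probability when every value is counted and the true rate equals b, since 2b × 0.5 = b. The simple exceedance rule is therefore imprecise even without the filter: it fires 39% of the time at b = 10% with no excess. The table shows one look at full enrolment, whereas the review is quarterly and earlier looks have fewer patients.

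**The case against.** The best defence is that laboratory toxicity is largely handled outside the adverse event definition. Section 3.4.1.2 requires a blood count with differential every two weeks for two months and then monthly, and requires laboratory examinations to be documented in the medical record and flow sheets, with no adverse event condition. Section 3.4.3 makes hematology and chemistry monitoring a separate safety component and assesses safety by the NCI criteria. Section 3.2.4 follows up abnormal values that led to interruption or discontinuation. Section 3.4.5.2 provides monthly review of significant toxicities and dose adjustments, with quarterly summaries to the committee. The stopping rule in Section 6.1.1 rests on discontinuation for toxicity. All of this stands, and it confines the gap to the rate comparison and to how safety is summarised.

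Two stronger readings are tempting. A reader might infer that asymptomatic grade 3 lymphopenia need not be recorded at all; the documentation requirement in Section 3.4.1.2 rules that out. A reader might also infer that the comparison is necessarily biased toward a finding of no excess. The documents do not support that: the brochure is unseen, Section 3.2.5 reports four electrolyte abnormalities as serious adverse reactions, so the separation is not complete, and Section 3.4.6 names no specific list. Nor do Table 3-1 and Section 3.4.3.1 contradict each other; one governs dosing and the other reporting.

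What the defence does not answer is that monitoring, charting and action-driven review produce no graded rate to set beside a reference rate.

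**Conclusion.** The point holds in limited form and is minor. Followed as written, the quarterly comparison can miss an excess of grade 3–4 lymphopenia and, to a lesser extent, anemia, and the safety objective can understate them. The size is not determinable from the documents. With a graded laboratory comparator and a true doubling at n = 60, counting half of the abnormalities instead of all lowers the chance of a flag from 0.97 to 0.39 at an assumed 10% reference rate, and from 0.86 to 0.35 at 5%. Those figures rest on assumed reference rates, an assumed doubling and assumed pass shares. With a different comparator the error could run the other way. The conclusion does not extend to hyperglycemia, hypophosphatemia or hypercholesterolemia at grade 3–4, most of which would probably count, nor to safety oversight as a whole.

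**What to change.** Keep the Section 3.4.3.1 rule for clinical adverse events. Add to Sections 3.4.3 and 3.4.6 that the hematology and chemistry results already collected under Sections 3.4.1.2 and 3.4.7.2 are graded by CTCAE version 3.0 on value alone, whatever the symptoms, treatment or judgement, and are summarised as worst grade per patient. State that each quarterly report compares this table with the brochure's laboratory-abnormality rates and compares adverse events with its adverse-reaction rates. The cost is some data entry and one more safety table. No new test or visit is needed, and the dosing rules are untouched.

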3.4.3.2 Serious adverse events

Information about all serious adverse events will be collected and recorded. To ensure patient safety each serious adverse event must also be reported to Novartis within 24 hours of learning of its occurrence. A serious adverse event is an undesirable sign, symptom or medical condition which:

- is fatal or life-threatening
- results in persistent or significant disability/incapacity
- constitutes a congenital anomaly/birth defect
- requires inpatient hospitalization or prolongation of existing hospitalization, unless hospitalization is for:
- routine treatment or monitoring of the studied indication, not associated with any deterioration in condition (specify what this includes)
- elective or pre-planned treatment for a pre-existing condition that is unrelated to the indication under study and has not worsened since the start of study drug
- treatment on an emergency outpatient basis for an event not fulfilling any of the definitions of a SAE given above and not resulting in hospital admission
- social reasons and respite care in the absence of any deterioration in the patient's general condition

- is medically significant, i.e., defined as an event that jeopardizes the patient or may require medical or surgical intervention to prevent one of the outcomes listed above

3.4.4 Novartis instructions for rapid notification of serious adverse events

The principal investigator has the obligation to report all serious adverse events to the FDA, IRB, and Novartis Pharmaceuticals Drug Safety and Epidemiology Department (DS&E).

All events reported to the FDA by the investigator are to be filed utilizing the Form FDA 3500A (MedWatch Form).

All events must be reported, by [contact]), to Novartis Pharmaceuticals DS&E Department within 24 hours of learning of its occurrence. This includes serious, related, labeled (expected) and serious, related, unlabeled (unexpected) adverse experiences. All deaths during treatment or within 30 days following completion of active protocol therapy must be reported within 5 working days.

Any serious adverse event occurring after the patient has provided informed consent and until 4 weeks after the patient has stopped study participation must be reported. This includes the period in which the study protocol interferes with the standard medical treatment given to a patient (e.g. treatment withdrawal during washout period, change in treatment to a fixed dose of concomitant medication).

Serious adverse events occurring more than 4 weeks after study discontinuation need only be reported if a relationship to the Novartis study drug (or therapy) is suspected.

For Comparator Drugs/Secondary Suspects (Concomitant Medications), all serious adverse experiences will be forwarded to the product manufacturer by the investigator.

3.4.5 Data Safety Monitoring Plan

3.4.5.1 Oversight and Monitoring Plan

The UCSF-CCC Data Safety Monitoring Committee (DSMC) is responsible for monitoring data quality and patient safety for all UCSF-CCC institutional clinical studies. A summary of DSMC activities for this study includes:

- Review of subject data in each cohort
- Quarterly review for progress and safety
- Review of all serious adverse events
- Minimum of a yearly audit

3.4.5.2 Monitoring and Reporting Guidelines

Investigators will conduct continuous review of data and patient safety at monthly study group or site committee meetings where the results of each patient's treatment are discussed and the discussion is documented in the minutes. The discussion will include the number of patients, significant toxicities as described in the protocol, doses adjustments, and observed responses. Quarterly summaries will be submitted to the DSMC for review. All grade 3-5

AE's and SAE's will be entered in the CCC Oncore database.

